POST DATABASE LOCK STATISTICAL ANALYSIS PLAN ADDENDUM			

1. BACKGROUND

This document details changes and / or additions to the planned statistical analyses for Opiant Pharmaceuticals, protocol “OPNT003-PK-002” study previously described in V1.0 of the Statistical Analysis Plan (SAP) dated 16-NOV-2021.

These amendments were made post database lock.

Rationale for Addendum:

- 1) In electrocardiogram assessments, results were summarized only by sequence. Since the data is collected during treatment periods, tables are updated to present results by both treatment and sequence.
- 2) Truncated mean, all subject, and individual subject plots through 4 hours postdose were added to illustrate early nalmefene exposure.

2. CHANGES TO EXISTING SAP

2.1 Change 1

2.1.1 Original text

6.11.4 Electrocardiogram Data

ECG values will be tabulated for Baseline, day 6, day 12 and EOS/ET, and change from Baseline to day 6 and 12, and change from Baseline to EOS by treatment sequence and overall. Parameters will be listed in the order given below and in units collected.

2.1.2 New text

6.11.4 Electrocardiogram Data

ECG values will be tabulated for Baseline, 20 mins, 1h and 6h, and change from baseline to 20 mins, 1h and 6h by treatment periods. In addition, ECG results will be tabulated for Baseline, EOS/ET, and change from Baseline to EOS/ET by treatment sequence and overall.

2.2 Change 2

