5 RANDOMIZATION

Twenty-four (24) healthy subjects will be randomly assigned to 6 sequences (4 subjects per sequence). Each subject will receive one of the 3 treatments in each of the 3 treatment periods.

The 6 sequences will be assigned as follows:

Sequence	Period 1	Period 2	Period 3
1	Treatment A	Treatment B	Treatment C
2	Treatment B	Treatment C	Treatment A
3	Treatment C	Treatment A	Treatment B
4	Treatment A	Treatment C	Treatment B
5	Treatment B	Treatment A	Treatment C
6	Treatment C	Treatment B	Treatment A

QMD Ref: Worldwide-TMP-ST-006-4.0 Effective: 12Aug2019	Governing QMD: Worldwide-SOP-ST-001
Confidentiality Statement	

This document is the property of Worldwide Clinical Trials Inc. and may not be duplicated, copied, altered or removed from company without prior approval from Worldwide Quality Assurance or in compliance with Worldwide Standard Operating Procedures.

Worldwide Clinical Trials Controlled Quality Management Document		
 WORLDWIDE CLINICAL TRIALS	Sponsor:	Opiant Pharmaceuticals
	Protocol Number:	OPNT003-PK-002

Where,

- Treatment A: 3 mg, one 0.1 mL spray in one nostril.
- Treatment B: 6 mg, one 0.1 mL spray in each nostril.
- Treatment C: 6 mg, two 0.1 mL sprays in one nostril.

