6.2.1 Study Period / Visits

Each visit as per study schedule will be mapped to treatment period and analysis visit for summary tables as given below. Listings will reflect actual period and visit as defined in protocol.

Collected Visit	Analysis Visit	Analysis Period
Screening	Screening	-
Day -1	Day -1	-
Day 1	Day 1	Period 1
Day 2	Day 2	Period 1
Day 3	Day 3	Period 1
Day 4	Day 4	Period 1
Day 5	Day 5	Period 1
Day 6	Day 6	Period 1
Day 7	Day 7	Period 2
Day 8	Day 8	Period 2
Day 9	Day 9	Period 2
Day 10	Day 10	Period 2
Day 11	Day 11	Period 2
Day 12	Day 12	Period 2
Day 13	Day 13	Period 3
Day 14	Day 14	Period 3
Day 15 (Discharge)	EOS / ET	-
Early Termination	EOS / ET	-
Follow-Up Phone Call	FUP	-

Any Discharge assessments taken more than once will be mapped as "DIS – Unscheduled" in listings.

QMD Ref: Worldwide-TMP-ST-006-4.0 Effective: 12Aug2019	Governing QMD: Worldwide-SOP-ST-001
Confidentiality Statement	
This document is the property of Worldwide Clinical Trials Inc. and may not be duplicated, copied, altered or removed from company without prior approval from Worldwide Quality Assurance or in compliance with Worldwide Standard Operating Procedures.	

Worldwide Clinical Trials Controlled Quality Management Document		
 WORLDWIDE CLINICAL TRIALS	Sponsor:	Opiant Pharmaceuticals

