6.3 Conventions

All clinical data listings, summaries, figures and statistical analyses will be generated using SAS (Version 9.4 or higher)¹.

Summaries of the clinical data will be presented by treatment and/or treatment sequence unless otherwise stated.

PK data listings, summaries, figures, and statistical analyses will be generated using Phoenix™ WinNonlin® (Version 8.1 or higher)² or SAS (Version 9.4 or higher)¹. PK concentration data will be summarized by treatment at each nominal sample time. PK parameter data will be summarized by treatment.

Treatment labels will be displayed as follows:

Treatment A

Treatment B

Treatment C

Footnotes describing each treatment will be provided in each output.

Treatment sequence labels will be displayed as follows:

Sequence 1

Sequence 2

Sequence 3

Sequence 4

Sequence 5

Sequence 6

QMD Ref: Worldwide-TMP-ST-006-4.0 Effective: 12Aug2019	Governing QMD: Worldwide-SOP-ST-001
Confidentiality Statement	

This document is the property of Worldwide Clinical Trials Inc. and may not be duplicated, copied, altered or removed from company without prior approval from Worldwide Quality Assurance or in compliance with Worldwide Standard Operating Procedures.

Worldwide Clinical Trials Controlled Quality Management Document		
 WORLDWIDE CLINICAL TRIALS	Sponsor: Protocol Number:	Opiant Pharmaceuticals OPNT003-PK-002

For safety assessment that are summarized by visit/timepoint, treatment and/or treatment sequence will be displayed in footnote as follows:

Treatment A: 3 mg (one 0.1 mL spray of 30 mg/mL nalmefene hydrochloride in one nostril)

Treatment B: 6 mg (one 0.1 mL sprays of 30 mg/mL nalmefene hydrochloride in each nostril)

Treatment C: 6 mg (two 0.1 mL sprays of 30 mg/mL nalmefene hydrochloride in one nostril)

“Sequence 1” represents subjects taking Treatment A in period 1, Treatment B in period 2 and Treatment C in period 3; “Sequence 2” represents subjects taking Treatment B in period 1, Treatment C in period 2 and Treatment A in period 3; “Sequence 3” represents subjects taking Treatment C in period 1, Treatment A in period 2 and Treatment B in period 3; “Sequence 4” represents subjects taking Treatment A in period 1, Treatment C in period 2 and Treatment B in period 3; “Sequence 5” represents subjects taking Treatment B in period 1, Treatment A in period 2 and Treatment C in period 3; “Sequence 6” represents subjects taking Treatment C in period 1, Treatment A in period 2 and Treatment B in period 3.

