6.11 Safety Analyses

The safety analyses will be presented by the treatment received for the Safety Population.

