5. CHANGES TO TFL SHELL

Previous version of TFL Shells: 1.0 / 16-Nov-2021

New version of TFL shells: 1.1 / 29-Mar-2022

QMD Ref: Worldwide-TMP-ST-008-2.0 Effective: 12Aug2019	Governing QMD: Worldwide-SOP-ST-001
Confidentiality Statement	
This document is the property of Worldwide Clinical Trials Inc. and may not be duplicated, copied, altered or removed from company without prior approval from Worldwide Quality Assurance or in compliance with Worldwide Standard Operating Procedures.	

Worldwide Clinical Trials Controlled Quality Management Document			
 WORLDWIDE CLINICAL TRIALS	Sponsor:	Opiant Pharmaceuticals	
	Protocol Number:	OPNT003-PK-002	
POST DATABASE LOCK STATISTICAL ANALYSIS PLAN ADDENDUM			

- Safety population definition was incorrect in few tables. It is corrected to “Safety Population includes subjects who took at least one dose of study drug”.
- All TFLs – In footnote, treatment sequence 6 definition was incorrect. It has been updated as “Sequence 6” represents subjects taking Treatment C in period 1, Treatment B in period 2 and Treatment A in period 3.
- Tables 14.3.1.1 and Table 14.3.1.8 – “Unknown” row is removed from relationship category.
- Table 14.3.1.2, Table 14.3.1.7, Table 14.3.1.8 and Listing 16.2.7.1 – MedDRA version is updated to 24.1.
- Table 14.3.4.7 – Title was incorrect. It has been updated to “Coagulation Data”.
- Table 14.3.5.1 and Table 14.3.5.2 - Reference listing number was incorrect. It has been corrected as ‘Listing 16.2.8.10’.
- Table 14.3.6.1 and Table 14.3.6.2 – Table is revamped to present ECG results by both treatment and treatment sequence.
- Table 14.3.6.1 and Table 14.3.6.2 - Reference listing number was incorrect. It has been corrected as ‘Listing 16.2.8.11’.
- Table 14.3.6.3 - Reference listing number was incorrect. It has been corrected as ‘Listing 16.2.8.12’.
- Table 14.3.6.4.1 – “Not Done / Missing” column has been added.
- Table 14.3.6.4.2 – “Not Done / Missing” row and column has been added.
- Table 14.3.6.4.1 and Table 14.3.6.4.2 - Reference listing number was incorrect. It has been corrected as ‘Listing 16.2.8.13’.
- Table 14.3.6.4.2 – “Not Done / Missing” row and column has been added.
- Table 14.3.6.5 - Reference listing number was incorrect. It has been corrected as ‘Listing 16.2.8.14’.
- Table 14.3.6.6 - Reference listing number was incorrect. It has been corrected as ‘Listing 16.2.8.15’.

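### The addendum's replacement ECG text groups the post-dose results by treatment period, contradicting its own statements that the ECG tables are by treatment and sequence

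*SAP*

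**What the plan says.** SAP V1.0, section 6.11.4, summarized ECG data by treatment sequence only. The post-database-lock addendum (2.1.2) replaces that text. Values at Baseline, 20 minutes, 1 hour and 6 hours are to be tabulated, with "change from baseline to 20 mins, 1h and 6h by treatment periods". A second sentence covers the end of the study: "change from Baseline to EOS/ET by treatment sequence and overall". Neither sentence gives a grouping by treatment alone.

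Two other places in the same addendum describe the same change:

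- Section 1, Rationale 1: "tables are updated to present results by both treatment and sequence".
- Section 5, for Tables 14.3.6.1 and 14.3.6.2: "Table is revamped to present ECG results by both treatment and treatment sequence".

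Two general rules in the main SAP were left unchanged by the addendum. The lead sentence of 6.11 reads "The safety analyses will be presented by the treatment received for the Safety Population". The display convention in 6.3 reads "Summaries of the clinical data will be presented by treatment and/or treatment sequence unless otherwise stated".

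**The concern.** The change was made because an ECG summary by sequence alone does not show results by treatment. In a six-sequence crossover, a summary by period does not show them either, because each period contains all three regimens. The sentence that governs the analysis therefore fails to deliver what the addendum says the change is for.

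ECG is a named safety endpoint (SAP 3.2), and safety and tolerability is the secondary objective (SAP 2). The 20-minute, 1-hour and 6-hour rows are the only planned ECG summaries within hours of a dose; the discharge ECG comes about 48 hours after the last one. A programmer who followed the sentence as written would produce columns that cannot separate 3 mg from 6 mg, and might also subtract a different baseline from the one intended.

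**Working it through.** **1. What a treatment period is in this SAP.** Section 5 separates treatment from period: "Each subject will receive one of the 3 treatments in each of the 3 treatment periods". Section 6.2.1 uses the term for calendar blocks: "Each visit as per study schedule will be mapped to treatment period and analysis visit for summary tables as given below". The table there assigns Days 1–6 to Period 1, Days 7–12 to Period 2 and Days 13–14 to Period 3. Where other safety sections want columns by regimen they say so: vital signs, nasal examination, NRS and smell test are all given by or per treatment. Read alone, the replacement ECG sentence groups by chronological period.

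**2. The statements side by side.**

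| Place | Grouping of ECG results |
|---|---|
| Addendum 1, Rationale 1 | treatment and sequence |
| Addendum 5, Tables 14.3.6.1 and 14.3.6.2 | treatment and sequence |
| Addendum 2.1.2, new 6.11.4, post-dose | treatment period |
| Addendum 2.1.2, new 6.11.4, EOS/ET | sequence and overall |

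The third row is the one that does not fit.

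**3. Who would be in each period column.** Inputs: six sequences with 4 subjects each (SAP 5), with Sequence 6 as C, B, A (SAP 5 and addendum 2.2.2). The plan's total is reproduced: 6 × 4 = 24.

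| Period | On A (3 mg) | On B (6 mg) | On C (6 mg) |
|---|---|---|---|
| 1 | Seq 1, 4: 2 × 4 = 8 | Seq 2, 5: 8 | Seq 3, 6: 8 |
| 2 | Seq 3, 5: 8 | Seq 1, 6: 8 | Seq 2, 4: 8 |
| 3 | Seq 2, 6: 8 | Seq 3, 4: 8 | Seq 1, 5: 8 |

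Each column has 8/24 = 33.3% at 3 mg and 16/24 = 66.7% at 6 mg. Grouped by treatment, each column has 24 subjects on one regimen.

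**4. What such a column would show.** Let a, b and c be the true mean changes on A, B and C. With no period or carryover effect, each period column has expectation (8a + 8b + 8c)/24 = (a + b + c)/3. The three columns are equal whatever a, b and c are. A period effect would make the columns differ, but that difference would reflect period, not regimen.

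The following effect sizes are assumed for illustration and are not in the documents. Take a = 0 and b = c = d, so each period column is 2d/3.

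| d (ms) | Period columns 1 / 2 / 3 | Treatment columns A / B / C |
|---|---|---|
| 5 | 3.33 / 3.33 / 3.33 | 0 / 5 / 5 |
| 10 | 6.67 / 6.67 / 6.67 | 0 / 10 / 10 |

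**5. Which baseline applies.** SAP 6.2.4 has two definitions. The general one is the last value before the first dose of the study. The period-specific one, the last value before that period's dose, is given only to variables summarized by treatment. If the post-dose ECG results are grouped by period, the condition for the second definition is not clearly met. Changes in Periods 2 and 3 could then be taken from a value before Day 1 rather than from the Day 6 or Day 12 ECG that the protocol synopsis schedules before those doses. The phrase can therefore alter computed changes as well as column headings.

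**The case against.** The strongest reply is that the phrase is merely loose. Rationale 1 gives the collection of data during treatment periods as the reason for presenting results by treatment, and the new text may just be echoing that wording. The new sentence pair also sets the post-dose results against an EOS/ET summary by sequence, which mirrors the treatment-and-sequence pairing in Rationale 1 and in section 5. On that view the intended meaning is by treatment, and the shells already reflect it.

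Most of this stands as evidence of intent. A reader might infer from the replacement sentence that the ECG tables do pool 3 mg and 6 mg in every column and that the ECG comparison between regimens is lost. The documents do not support that. The only description of the revised layout says by treatment and sequence, the table titles name no grouping, and the shells themselves are not in the documents supplied. Nor do the documents support calling these time points near peak exposure, since they give no Tmax value.

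The reply does not remove the contradiction. The lead sentence of 6.11 does not settle the matter: it was already in V1.0, and Rationale 1 confirms that ECG results were nonetheless summarized only by sequence, so the specific text prevailed over the general one. The 6.3 convention yields where something else is stated. Nothing says that the shells take precedence over the SAP text, and equally nothing says that the replacement sentence takes precedence over the rationale and the shell note.

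The consequence is also limited. No inferential ECG comparison is planned. All ECG data are listed (Listing 16.2.8.11), and listings are sorted by sequence and subject, so the regimen behind every record can be recovered.

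**Conclusion.** The replacement 6.11.4 text is wrong as written: its grouping of the post-dose ECG results contradicts the addendum's own rationale and its description of Tables 14.3.6.1 and 14.3.6.2. What is established is an inconsistency within the addendum, not a defect in the tables.

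If the sentence were applied literally, the regimen contrast between columns would have expectation zero. That result rests on the planned 4 subjects per sequence, full completion, and no period or carryover effect. Dropouts would unbalance the 8/8/8 split, but the regimens would still be mixed within each column.

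Severity is low. These are descriptive safety tables, the shells are already described as by treatment, and no pharmacokinetic analysis, sample size, power or alpha figure depends on them. The correction is still worth making because it also settles the baseline.

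**What to change.** In the new 6.11.4 text, replace the grouping by treatment periods with grouping by treatment (A, B, C) for the 20-minute, 1-hour and 6-hour values and changes. Add one sentence stating that the period-specific baseline of SAP 6.2.4 applies to these changes. It would help to name the source ECGs, because the visit mapping in 6.2.1 places Day 6 in Period 1 and Day 12 in Period 2. Keep Baseline to EOS/ET by treatment sequence and overall. Confirm that the post-dose rows of Tables 14.3.6.1 and 14.3.6.2 have treatment columns, as addendum section 5 describes.

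The cost is one phrase and one sentence. No new data are needed and, if the shells are as described, no change to the tables. As the addendum already postdates database lock, the correction can be made in a revised addendum or recorded in the CSR as SAP section 7 provides.

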2.2.1 Original text

6.3 Conventions

“Sequence 1” represents subjects taking Treatment A in period 1, Treatment B in period 2 and Treatment C in period 3; “Sequence 2” represents subjects taking Treatment B in period 1, Treatment C in period 2 and Treatment A in period 3; “Sequence 3” represents subjects taking Treatment C in period 1, Treatment A in period 2 and Treatment B in period

QMD Ref: Worldwide-TMP-ST-008-2.0 Effective: 12Aug2019	Governing QMD: Worldwide-SOP-ST-001
Confidentiality Statement	
This document is the property of Worldwide Clinical Trials Inc. and may not be duplicated, copied, altered or removed from company without prior approval from Worldwide Quality Assurance or in compliance with Worldwide Standard Operating Procedures.	

Worldwide Clinical Trials Controlled Quality Management Document			
 WORLDWIDE CLINICAL TRIALS	Sponsor:	Opiant Pharmaceuticals	
	Protocol Number:	OPNT003-PK-002	
POST DATABASE LOCK STATISTICAL ANALYSIS PLAN ADDENDUM			

3; “Sequence 4” represents subjects taking Treatment A in period 1, Treatment C in period 2 and Treatment B in period 3; “Sequence 5” represents subjects taking Treatment B in period 1, Treatment A in period 2 and Treatment C in period 3; **“Sequence 6” represents subjects taking Treatment C in period 1, Treatment A in period 2 and Treatment B in period 3.**

2.2.2 New text

6.3 Conventions

“Sequence 1” represents subjects taking Treatment A in period 1, Treatment B in period 2 and Treatment C in period 3; “Sequence 2” represents subjects taking Treatment B in period 1, Treatment C in period 2 and Treatment A in period 3; “Sequence 3” represents subjects taking Treatment C in period 1, Treatment A in period 2 and Treatment B in period 3; “Sequence 4” represents subjects taking Treatment A in period 1, Treatment C in period 2 and Treatment B in period 3; “Sequence 5” represents subjects taking Treatment B in period 1, Treatment A in period 2 and Treatment C in period 3; **“Sequence 6” represents subjects taking Treatment C in period 1, Treatment B in period 2 and Treatment A in period 3.**

2.3 Change 3

Titles of few outputs were not matching with SAP section 9 List of Tables, Figures and Listings. SAP is updated to have the same names of TFLs as in TFL Mock Shells.

3. ADDITIONS TO EXISTING SAP

3.1 Addition 1

Truncated mean, all subject, and individual subject concentration-time profiles through 4 hours postdose were added to illustrate early nalmefene exposure.

4. CHANGES TO TABLES, FIGURES AND LISTINGS (TFL) SHELL TABLE OF CONTENT (TOC) WITHIN SAP

New TOC attached:

yes
 no

5. CHANGES TO TFL SHELL

Previous version of TFL Shells: 1.0 / 16-Nov-2021

New version of TFL shells: 1.1 / 29-Mar-2022

QMD Ref: Worldwide-TMP-ST-008-2.0 Effective: 12Aug2019	Governing QMD: Worldwide-SOP-ST-001
Confidentiality Statement	
This document is the property of Worldwide Clinical Trials Inc. and may not be duplicated, copied, altered or removed from company without prior approval from Worldwide Quality Assurance or in compliance with Worldwide Standard Operating Procedures.	

Worldwide Clinical Trials Controlled Quality Management Document			
 WORLDWIDE CLINICAL TRIALS	Sponsor:	Opiant Pharmaceuticals	
	Protocol Number:	OPNT003-PK-002	
POST DATABASE LOCK STATISTICAL ANALYSIS PLAN ADDENDUM			

- Safety population definition was incorrect in few tables. It is corrected to “Safety Population includes subjects who took at least one dose of study drug”.
- All TFLs – In footnote, treatment sequence 6 definition was incorrect. It has been updated as “Sequence 6” represents subjects taking Treatment C in period 1, Treatment B in period 2 and Treatment A in period 3.
- Tables 14.3.1.1 and Table 14.3.1.8 – “Unknown” row is removed from relationship category.
- Table 14.3.1.2, Table 14.3.1.7, Table 14.3.1.8 and Listing 16.2.7.1 – MedDRA version is updated to 24.1.
- Table 14.3.4.7 – Title was incorrect. It has been updated to “Coagulation Data”.
- Table 14.3.5.1 and Table 14.3.5.2 - Reference listing number was incorrect. It has been corrected as ‘Listing 16.2.8.10’.
- Table 14.3.6.1 and Table 14.3.6.2 – Table is revamped to present ECG results by both treatment and treatment sequence.
- Table 14.3.6.1 and Table 14.3.6.2 - Reference listing number was incorrect. It has been corrected as ‘Listing 16.2.8.11’.
- Table 14.3.6.3 - Reference listing number was incorrect. It has been corrected as ‘Listing 16.2.8.12’.
- Table 14.3.6.4.1 – “Not Done / Missing” column has been added.
- Table 14.3.6.4.2 – “Not Done / Missing” row and column has been added.
- Table 14.3.6.4.1 and Table 14.3.6.4.2 - Reference listing number was incorrect. It has been corrected as ‘Listing 16.2.8.13’.
- Table 14.3.6.4.2 – “Not Done / Missing” row and column has been added.
- Table 14.3.6.5 - Reference listing number was incorrect. It has been corrected as ‘Listing 16.2.8.14’.
- Table 14.3.6.6 - Reference listing number was incorrect. It has been corrected as ‘Listing 16.2.8.15’.
- Figures 14.4.1.1, 14.4.2.1, and 14.4.3.1 for truncated mean, all subject, and individual subject concentration-time profiles were added.
- Listing 16.2.4.1 – there was a spelling mistake in title. It has been updated to “Demographic Data”.
- Listing 16.2.4.3 – WHODD version updated as “Sep 2021”.
- Listing 16.2.8.8 – “Occurrence” column has been added. “Category” column moved prior to that.

QMD Ref: Worldwide-TMP-ST-008-2.0 Effective: 12Aug2019	Governing QMD: Worldwide-SOP-ST-001
Confidentiality Statement This document is the property of Worldwide Clinical Trials Inc. and may not be duplicated, copied, altered or removed from company without prior approval from Worldwide Quality Assurance or in compliance with Worldwide Standard Operating Procedures.	

Worldwide Clinical Trials Controlled Quality Management Document			
 WORLDWIDE CLINICAL TRIALS	Sponsor:	Opiant Pharmaceuticals	
	Protocol Number:	OPNT003-PK-002	
POST DATABASE LOCK STATISTICAL ANALYSIS PLAN ADDENDUM			

- 14.3.6.3 – Title was incorrect. It has been updated to “Physical Examination Data, Shift Summary”.
- 14.3.6.4.2 – Title was incorrect. It has been updated to “Nasal Cavity Examination Data, Shift Summary”.

Table Number	Table Title	Validation Method	Shell Number (if repeat)
Items in bold are not table titles but references to the section headings within eCTD.			
14.1	Demographics Data		
14.1.1	Disposition		
14.1.1.1	Subject Disposition, Analysis Populations – All Subjects	IP	-
14.1.2	Demographics		
14.1.2.1	Subject Demographics - Safety Population	IP	-
14.1.2.2	Subject Demographics - PK Evaluation Population	IP	14.1.2.2
14.1.3	Baseline Characteristics		
	Not Applicable		
14.2	Efficacy Data		
	Not Applicable		
14.3	Safety Data		
14.3.1	Displays of Adverse Events		
14.3.1.1	Adverse Events, Overall Summary – Safety Population	IP	-

QMD Ref: Worldwide-TMP-ST-008-2.0 Effective: 12Aug2019	Governing QMD: Worldwide-SOP-ST-001
Confidentiality Statement	

This document is the property of Worldwide Clinical Trials Inc. and may not be duplicated, copied, altered or removed from company without prior approval from Worldwide Quality Assurance or in compliance with Worldwide Standard Operating Procedures.

Worldwide Clinical Trials Controlled Quality Management Document			
 WORLDWIDE CLINICAL TRIALS	Sponsor:	Opiant Pharmaceuticals	
	Protocol Number:	OPNT003-PK-002	
POST DATABASE LOCK STATISTICAL ANALYSIS PLAN ADDENDUM			

Table Number	Table Title	Validation Method	Shell Number (if repeat)
14.3.1.2	Adverse Events, Treatment Emergent Adverse Events by SOC and PT – Safety Population	IP	-
14.3.1.3	Adverse Events, Related Treatment Emergent Adverse Events by SOC and PT – Safety Population	IP	14.3.1.2
14.3.1.4	Adverse Events, Serious Treatment Emergent Adverse Events by SOC and PT – Safety Population	IP	14.3.1.2
14.3.1.5	Adverse Events, Related Serious Treatment Emergent Adverse Events by SOC and PT – Safety Population	IP	14.3.1.2
14.3.1.6	Adverse Events, Treatment Emergent Adverse Events leading to Early Withdrawal by SOC and PT – Safety Population	IP	14.3.1.2
14.3.1.7	Adverse Events, Treatment Emergent Adverse Events by SOC, PT and Maximum Severity - Safety Population	IP	-
14.3.1.8	Adverse Events, Treatment Emergent Adverse Events by SOC, PT and Closest Relationship - Safety Population	IP	-
14.3.2	Listings of Deaths, Other Serious and Significant Adverse Events		
14.3.2.1	Serious Adverse Event Data – Safety Population	IP	16.2.7.1
14.3.2.2	Adverse Event Leading to Death – Safety Population	IP	16.2.7.1
14.3.2.3	Adverse Event Leading to Early Withdrawal – Safety Population	IP	16.2.7.1
14.3.3	Narratives of Deaths, Other Serious and Certain Other Significant Adverse Events		

QMD Ref: Worldwide-TMP-ST-008-2.0 Effective: 12Aug2019	Governing QMD: Worldwide-SOP-ST-001
Confidentiality Statement	

This document is the property of Worldwide Clinical Trials Inc. and may not be duplicated, copied, altered or removed from company without prior approval from Worldwide Quality Assurance or in compliance with Worldwide Standard Operating Procedures.

Worldwide Clinical Trials Controlled Quality Management Document			
 WORLDWIDE CLINICAL TRIALS	Sponsor:	Opiant Pharmaceuticals	
	Protocol Number:	OPNT003-PK-002	
POST DATABASE LOCK STATISTICAL ANALYSIS PLAN ADDENDUM			

Table Number	Table Title	Validation Method	Shell Number (if repeat)
14.3.4	Abnormal Laboratory Values		
14.3.4.1	Hematology Data, Descriptive Statistics - Safety Population	IP	-
14.3.4.2	Clinical Chemistry Data, Descriptive Statistics - Safety Population	IP	14.3.4.1
14.3.4.3	Coagulation Data, Descriptive Statistics - Safety Population	IP	14.3.4.1
14.3.4.4	Urinalysis Data, Descriptive Statistics - Safety Population	IP	14.3.4.1
14.3.4.5	Hematology Data, Shift Summary - Safety Population	IP	-
14.3.4.6	Clinical Chemistry Data, Shift Summary - Safety Population	IP	14.3.4.5
14.3.4.7	Coagulation Data, Shift Summary - Safety Population	IP	14.3.4.5
14.3.4.8	Urinalysis Data, Shift Summary - Safety Population	IP	16.2.8.1
14.3.4.9	Out of Range Laboratory Data – Safety Population	IP	-
14.3.5	Vital Signs and Physical Examination		
14.3.5.1	Vital Signs, Descriptive Statistics – Safety Population	IP	-
14.3.5.2	Vital Signs, Shift Summary – Safety Population	IP	-
14.3.6	Other Safety		
14.3.6.1	12 Lead ECG, Descriptive Statistics - Safety Population	IP	-

QMD Ref: Worldwide-TMP-ST-008-2.0 Effective: 12Aug2019	Governing QMD: Worldwide-SOP-ST-001
Confidentiality Statement	
This document is the property of Worldwide Clinical Trials Inc. and may not be duplicated, copied, altered or removed from company without prior approval from Worldwide Quality Assurance or in compliance with Worldwide Standard Operating Procedures.	

Worldwide Clinical Trials Controlled Quality Management Document			
 WORLDWIDE CLINICAL TRIALS	Sponsor:	Opiant Pharmaceuticals	
	Protocol Number:	OPNT003-PK-002	
POST DATABASE LOCK STATISTICAL ANALYSIS PLAN ADDENDUM			

Table Number	Table Title	Validation Method	Shell Number (if repeat)
14.3.6.2	12 Lead ECG, Shift Summary - Safety Population	IP	-
14.3.6.3	Physical Examination Data, Shift Summary - Safety Population	IP	-
14.3.6.4.1	Nasal Cavity Examination Data, Descriptive Statistics - Safety Population	IP	-
14.3.6.4.2	Nasal Cavity Examination Data, Shift Summary - Safety Population	IP	-
14.3.6.5	Numerical Rating Scale Data, Descriptive Statistics - Safety Population	IP	-
14.3.6.6	Brief Smell Identification Score Data, Descriptive Statistics - Safety Population	IP	-
14.3.7	Concomitant Medication		
	Not Applicable		
14.4	PK Tables		
14.4.1	Descriptive Statistics for Concentration-Time Data of Nalmefene after IN Administration of 3 mg Nalmefene HCl in One Nostril (T1, Treatment A), 3 mg (6 mg Total Dose) Nalmefene HCl in Each Nostril (Treatment B, T2), and 6 mg Nalmefene HCl in One Nostril (Treatment C, T3) – PK Evaluation Population	IP	-
14.4.2	Plasma PK Parameters of Nalmefene after IN Administration of 3 mg Nalmefene HCl in One Nostril (T1, Treatment A), 3 mg (6 mg Total Dose) Nalmefene HCl in Each Nostril (Treatment B, T2), and 6 mg	IP	-

QMD Ref: Worldwide-TMP-ST-008-2.0 Effective: 12Aug2019	Governing QMD: Worldwide-SOP-ST-001
Confidentiality Statement	

This document is the property of Worldwide Clinical Trials Inc. and may not be duplicated, copied, altered or removed from company without prior approval from Worldwide Quality Assurance or in compliance with Worldwide Standard Operating Procedures.

Worldwide Clinical Trials Controlled Quality Management Document			
 WORLDWIDE CLINICAL TRIALS	Sponsor:	Opiant Pharmaceuticals	
	Protocol Number:	OPNT003-PK-002	
POST DATABASE LOCK STATISTICAL ANALYSIS PLAN ADDENDUM			

Table Number	Table Title	Validation Method	Shell Number (if repeat)
	Nalmefene HCl in One Nostril (Treatment C, T3) – PK Evaluation Population		
14.4.3	Plasma PK Partial AUCs of Nalmefene after IN Administration of 3 mg Nalmefene HCl in One Nostril (T1, Treatment A), 3 mg (6 mg Total Dose) Nalmefene HCl in Each Nostril (Treatment B, T2), and 6 mg Nalmefene HCl in One Nostril (Treatment C, T3) – PK Population	IP	-
14.4.4	Plasma Dose-Normalized Parameters of Nalmefene after IN Administration of 3 mg Nalmefene HCl in One Nostril (T1, Treatment A), 3 mg (6 mg Total Dose) Nalmefene HCl in Each Nostril (Treatment B, T2), and 6 mg Nalmefene HCl in One Nostril (Treatment C, T3) – PK Population	IP	-
14.4.5	Dose-Normalized Plasma PK Partial AUCs of Nalmefene after IN Administration of 3 mg Nalmefene HCl in One Nostril (T1, Treatment A), 3 mg (6 mg Total Dose) Nalmefene HCl in Each Nostril (Treatment B, T2), and 6 mg Nalmefene HCl in One Nostril (Treatment C, T3) – PK Population	IP	-
14.4.6	Statistical Analysis of the Natural Log-Transformed, Dose-Normalized Exposure Parameters of Nalmefene Comparing 6 mg Nalmefene Hydrochloride in One Nostril (Treatment C, T3, Test) and 3 mg Nalmefene Hydrochloride in One Nostril (Treatment A, T1, Reference) – PK Evaluation Population	IP	-
14.4.7	Statistical Analysis of the Natural Log-Transformed, Dose-Normalized Exposure Parameters of Nalmefene Comparing 3 mg Nalmefene Hydrochloride in Each Nostril (6 mg Total Dose, Treatment B, T2, Test) and	IP	-

QMD Ref: Worldwide-TMP-ST-008-2.0 Effective: 12Aug2019	Governing QMD: Worldwide-SOP-ST-001
Confidentiality Statement	

This document is the property of Worldwide Clinical Trials Inc. and may not be duplicated, copied, altered or removed from company without prior approval from Worldwide Quality Assurance or in compliance with Worldwide Standard Operating Procedures.

Worldwide Clinical Trials Controlled Quality Management Document			
 WORLDWIDE CLINICAL TRIALS	Sponsor:	Opiant Pharmaceuticals	
	Protocol Number:	OPNT003-PK-002	
POST DATABASE LOCK STATISTICAL ANALYSIS PLAN ADDENDUM			

Table Number	Table Title	Validation Method	Shell Number (if repeat)
	3 mg Nalmefene Hydrochloride in One Nostril (Treatment A, T1, Reference) – PK Evaluation Population		
14.4.8	Statistical Analysis of the Natural Log-Transformed, Dose-Normalized Exposure Parameters of Nalmefene Comparing 3 mg Nalmefene Hydrochloride in Each Nostril (6 mg Total Dose, Treatment B, T2, Test) and 6 mg Nalmefene Hydrochloride in One Nostril (Treatment C, T3, Reference) – PK Evaluation Population	IP	-
14.5	PD Tables		
14.6	Other Data		

QMD Ref: Worldwide-TMP-ST-008-2.0 Effective: 12Aug2019	Governing QMD: Worldwide-SOP-ST-001
Confidentiality Statement	

This document is the property of Worldwide Clinical Trials Inc. and may not be duplicated, copied, altered or removed from company without prior approval from Worldwide Quality Assurance or in compliance with Worldwide Standard Operating Procedures.

Worldwide Clinical Trials Controlled Quality Management Document			
 WORLDWIDE CLINICAL TRIALS	Sponsor:	Opiant Pharmaceuticals	
	Protocol Number:	OPNT003-PK-002	
POST DATABASE LOCK STATISTICAL ANALYSIS PLAN ADDENDUM			

Figure Number	Figure Title	Validation Method	Shell Number (if repeat)
14.4.1	Nalmefene Concentration-Time Data, Mean Profiles on Linear and Semi-Logarithmic Scales after Intranasal (IN) Administrations of 3 mg Nalmefene Hydrochloride in One Nostril (T1), 2 x 3 mg Nalmefene Hydrochloride in Each Nostril (6 mg Total Dose, T2), and 6 mg Nalmefene Hydrochloride in One Nostril (T3) – PK Evaluation Population	IP	-
14.4.1.1	Nalmefene Concentration-Time Data, Mean Profiles on Linear and Semi-Logarithmic Scales after Intranasal (IN) Administrations of 3 mg Nalmefene Hydrochloride in One Nostril (T1), 3 mg Nalmefene Hydrochloride in Each Nostril (6 mg Total Dose, T2), and 6 mg Nalmefene Hydrochloride in One Nostril (T3) (X-Axis Truncated to 4 h Post Dose) – PK Evaluation Population	IP	
14.4.2	Nalmefene Concentration-Time Data, All Subject Profiles on Linear and Semi-Logarithmic Scales after Intranasal (IN) Administrations of 3 mg Nalmefene Hydrochloride in One Nostril (T1), 2 x 3 mg Nalmefene Hydrochloride in Each Nostril (6 mg Total Dose, T2), and 6 mg Nalmefene Hydrochloride in One Nostril (T3) – PK Evaluation Population	IP	-
14.4.2.1	Nalmefene Concentration-Time Data, All Subject Profiles on Linear and Semi-Logarithmic Scales after Intranasal (IN) Administrations of 3 mg Nalmefene Hydrochloride in One Nostril (T1), 3 mg Nalmefene Hydrochloride in Each Nostril (6 mg Total Dose, T2), and 6 mg Nalmefene Hydrochloride in One Nostril (T3) (X-Axis Truncated to 4 h Post Dose) – PK Evaluation Population	IP	
14.4.3	Nalmefene Concentration-Time Data, Individual Profiles on Linear and Semi-Logarithmic Scales after	IP	-

QMD Ref: Worldwide-TMP-ST-008-2.0 Effective: 12Aug2019	Governing QMD: Worldwide-SOP-ST-001
Confidentiality Statement	

This document is the property of Worldwide Clinical Trials Inc. and may not be duplicated, copied, altered or removed from company without prior approval from Worldwide Quality Assurance or in compliance with Worldwide Standard Operating Procedures.

Worldwide Clinical Trials Controlled Quality Management Document			
 WORLDWIDE CLINICAL TRIALS	Sponsor:	Opiant Pharmaceuticals	
	Protocol Number:	OPNT003-PK-002	
POST DATABASE LOCK STATISTICAL ANALYSIS PLAN ADDENDUM			

Figure Number	Figure Title	Validation Method	Shell Number (if repeat)
	Intranasal (IN) Administrations of 3 mg Nalmefene Hydrochloride in One Nostril (T1), 2 x 3 mg Nalmefene Hydrochloride in Each Nostril (6 mg Total Dose, T2), and 6 mg Nalmefene Hydrochloride in One Nostril (T3) – PK Evaluation Population		
14.4.3.1	Nalmefene Concentration-Time Data, Individual Profiles on Linear and Semi-Logarithmic Scales after Intranasal (IN) Administrations of 3 mg Nalmefene Hydrochloride in One Nostril (T1), 3 mg Nalmefene Hydrochloride in Each Nostril (6 mg Total Dose, T2), and 6 mg Nalmefene Hydrochloride in One Nostril (T3) (X-Axis Truncated to 4 h Post Dose) – PK Evaluation Population	IP	
14.4.4	Concentration-Time Profiles for Nalmefene with Linear Regression for Estimating the Terminal Elimination Rate - PK Evaluation Population	IP	-

QMD Ref: Worldwide-TMP-ST-008-2.0 Effective: 12Aug2019	Governing QMD: Worldwide-SOP-ST-001
Confidentiality Statement	

This document is the property of Worldwide Clinical Trials Inc. and may not be duplicated, copied, altered or removed from company without prior approval from Worldwide Quality Assurance or in compliance with Worldwide Standard Operating Procedures.

Worldwide Clinical Trials Controlled Quality Management Document			
 WORLDWIDE CLINICAL TRIALS	Sponsor:	Opiant Pharmaceuticals	
	Protocol Number:	OPNT003-PK-002	
POST DATABASE LOCK STATISTICAL ANALYSIS PLAN ADDENDUM			

Listing Number	Listing Title	Validation Method	Shell Number (if repeat)
16.2	Subject Data Listings		
16.2.1	Discontinued Subjects		
16.2.1.1	Subject Disposition – All Subjects	IP	-
16.2.2	Protocol Deviations		
16.2.2.1	Protocol Deviations – Safety Population	IP	-
16.2.3	Subjects Excluded from the Efficacy Analyses		
16.2.3.1	Analysis Populations – All Subjects	IP	-
16.2.4	Demographic Data		
16.2.4.1	Demographic Data – Safety Population	IP	-
16.2.4.2	Medical History – Safety Population	IP	-
16.2.4.3	Prior and Concomitant Medications - Safety Population	IP	-
16.2.5	Compliance and / or Drug Concentration Data		
16.2.5.1	Exposure Data – Safety Population	IP	-
16.2.6	Individual Efficacy Response Data		
16.2.6.1	Nalmefene Concentration-Time Data Listing – Safety Population	IP	-

QMD Ref: Worldwide-TMP-ST-008-2.0 Effective: 12Aug2019	Governing QMD: Worldwide-SOP-ST-001
Confidentiality Statement	
This document is the property of Worldwide Clinical Trials Inc. and may not be duplicated, copied, altered or removed from company without prior approval from Worldwide Quality Assurance or in compliance with Worldwide Standard Operating Procedures.	

Worldwide Clinical Trials Controlled Quality Management Document			
 WORLDWIDE CLINICAL TRIALS	Sponsor:	Opiant Pharmaceuticals	
	Protocol Number:	OPNT003-PK-002	
POST DATABASE LOCK STATISTICAL ANALYSIS PLAN ADDENDUM			

Listing Number	Listing Title	Validation Method	Shell Number (if repeat)
16.2.6.2	Terminal Elimination Rate of Nalmefene in Plasma for Individual Subjects – PK Evaluation Population	IP	-
16.2.6.3	PK Output Text – PK Evaluation Population	IP	-
16.2.6.4	SAS Output Text (ANOVA) – PK Evaluation Population	IP	-
16.2.7	Adverse Event Listings		
16.2.7.1	Adverse Event Data – Safety Population	IP	-
16.2.8	Individual Laboratory Measurements and Other Safety		
16.2.8.1	Hematology Data – Safety Population	IP	-
16.2.8.2	Serum Chemistry Data – Safety Population	IP	16.2.8.1
16.2.8.3	Coagulation Data – Safety Population	IP	16.2.8.1
16.2.8.4	Urinalysis Data – Safety Population	IP	16.2.8.1
16.2.8.5	Drug, Alcohol and Cotinine Screen – Safety Population	IP	-
16.2.8.6	Serology Data – Safety Population	IP	16.2.8.5
16.2.8.7	Pregnancy Test Data – Safety Population	IP	-
16.2.8.8	Substance Use Data - Safety Population	IP	-
16.2.8.9	COVID-19 PCR Test Data – Safety Population	IP	-
16.2.8.10	Vital Signs Data – Safety Population	IP	-

